Hematology (including Reticulocyte counts), Blood chemistry (free Hgb and haptoglobin), LDH level (b)	X						X			X			X			X			X					X		X		X		X	
Urinalysis (b)	X						X			X			X			X			X					X		X		X		X	
Number of blood transfusions																									X						
PNH type III RBCs by flow cytometry (b)																									X						X

Commercially Confidential Information

PK blood collection (b) _____ X
a: Serum pregnancy test required at screening of Period 1, urine pregnancy test at further time points. Only for post-menopausal women, the hormone measurement (FSH) to confirm post menopausal status required at screening of Period 1
b: Ad-hoc sampling at unscheduled visits allowed (e.g. safety reasons, loss of efficacy, etc)

Assessment schedule for patients participating in Period 4

Study epoch	Treatment								Study Completion ⁴
	Treatment Period 4 (Extension Period 4)								
Study phase	601	602	603	604	605	606	607	608	
Visit Numbers (internal use only)	V1001	V1002	V1003	V1004	V1005	V1006	V1007	V1008	
Period 4 visit number									
Day	1	15	29	36	43	57	85	141	
Visit window	-	-	±1	±1	±1	±2	±2	±28	Visit 777 Day 148 (1 week after last LNP023 dose) ±28
Inclusion/exclusion for period 4*	S ¹								
Physical examination	S ¹	S	S	S	S	S	S	S	S
Pregnancy test	X ¹		X			X	X		X
LFG316 administration	X	X							
LNP023 administration ⁵				X ³					
Body weight	X ¹								X
Body temperature	X ¹	X	X	X	X	X	X	X	X
Blood pressure / Pulse rate	X ¹								X
ECG evaluation	X ¹								X
Hematology and blood chemistry	X ¹	X	X	X	X	X	X	X	X
Blood hormones	X ¹		X			X	X	X	X
Urinalysis	X ¹								X
Number of blood transfusions					X				

Commercially Confidential Information

LNP023 PK		X ²		X ²					
Adverse Events				As required					X
Concomitant meds/Therapies				As required					X
Comments				As required					X

* Eligibility needs to be confirmed before first dose of LNP023 is administered

S: Captured as Source Data only

¹Pre-LNP023 and LFG316 dose

² Two time points: pre LNP023 morning dose and 2h post morning LNP023 dose

³ B.i.d. administration

⁴ Safety follow up call should happen approximately 1 month after last LNP023 dose is administered for patients that do not roll over into CLNP023C12001B

⁵ Patient diary will be implemented to collect information on missing LNP023 doses

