Patients participating in extension period 3 will roll over from the last dosing visit of period 2 to the first visit (which includes drug administration) of period 3. The same dosing interval applied in Period 1 and 2 will be applied between the last dosing visit of Period 2 and the first visit of Period 3.

Period 4 can be initiated as directed by Sponsor and will last approximately 21 weeks. During the first 4 weeks patients will continue to receive LFG316 20 mg/kg every two weeks (total of two administrations) in addition to oral administration of LNP023 200 mg b.i.d. After 4 weeks, patients will discontinue LFG316 and will proceed with LNP023 200 mg b.i.d. monotherapy for approximately 16 weeks (+/- 28 days). Patients who participate in period 4 can join the long-term extension study CLNP023C12001B as soon as their eligibility is confirmed and study CLNP023C12001B is open to receive patients. There should be no LNP023 treatment gap between the studies. Please refer to [Section 7.1](#) for guidance regarding safety monitoring and LNP023 down-titration in case of LNP023 treatment discontinuation.

Commercially Confidential Information

For patients not participating in the period 4, the extension period 3 will be followed by a Study Completion evaluation approximately 8 weeks after the last drug administration. Patients who discontinue treatment prematurely during any of the study periods will be followed for 8 weeks after discontinuation, and will similarly undergo a study completion visit. The 8 weeks follow-up period will start the day after the last drug administration (both for patients completing treatment and patients prematurely discontinuing), and will comprise one visit after approximately 4 weeks, and a study completion visit after approximately 8 weeks from the last drug administration. Safety assessments will include physical examinations, ECG, vital signs, standard clinical laboratory evaluations (hematology, blood chemistry, urinalysis) and adverse event monitoring.

Patients participating in period 4, will complete their Study Completion evaluation approximately one week after last LNP023 treatment administered as a part of this study.

Figure 3-1 Study design

*Period 4 is applicable only for the patients who are potentially eligible and wish to participate in the long-term extension study CLNP023C12001B

**+/-28 days

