Based on its mechanism of action, the main potential risk of LNP023 is infection-related. An intact complement system is particularly important for the defense against encapsulated bacteria (e.g., *Neisseria meningitidis*, *Streptococcus pneumoniae*, and *Hemophilus influenzae*). Patients with factor B loss-of-function mutations are more susceptible to such infections ([Slade et al 2013](#)). The mitigation strategy is to vaccinate patients before the first LNP023 treatment. If LNP023 treatment has to start earlier than 2 weeks post vaccination, prophylactic antibiotic treatment must be initiated. Data suggest that the protective effect of vaccination is maintained after blockade of the AP, but not after C5 blockade ([Konar and Granoff 2017](#)). In addition, patients will be instructed to contact the Investigator immediately in case of any signs or symptoms of infection (listed on a “Patient Card” for participant awareness), and relevant AEs will be reviewed on a regular basis.

Commercially Confidential Information

Regarding the potential safety risks mentioned above, to date, there have been no serious infections reported in PNH patients, although a SUSAR of pneumococcal pneumonia and sepsis was recently reported on the C3 glomerulopathy trial in a severely immunosuppressed patient with a history of renal transplantation (see [Section 1.1.1.3.2](#)). Considering implementation of the vaccinations and close monitoring, the risk for serious infection during LNP023 treatment is still considered to be low. Finally, there have been no serious adverse events related to the other potential risks in any of the clinical studies.

Commercially Confidential Information

Commercially Confidential Information

The risk to subjects in this trial receiving LNP023 will be minimized by adherence to the eligibility criteria, close clinical monitoring, pre-defined stopping rules, periodic review of the safety data, and guidance for the investigators in the Investigator's Brochure.

To note, women of child bearing potential (WOCBP) must be informed that taking the study treatment may involve unknown risks to the fetus if pregnancy were to occur during the study, and agree that in order to participate in the study they must adhere to the highly effective contraception requirements outlined in the Exclusion Criteria. If there is any question that the subject will not reliably comply, they should not be entered or continue in the study.

4 Population

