6.7 Treatment exposure and compliance

LFG316 will be administered at the dose level of 20 mg/kg via intravenous infusion by the Investigator or designated study staff over approximately 2 hours in Period 1 and between 40 minutes and 2 hours in Periods 2 and 3 (please refer to Pharmacy Manual), and therefore compliance with the planned treatment will be assumed since infusions will be carried out under close medical supervision at the study sites. Although infusion reactions have not been observed with LFG316 to date, close medical supervision at the study site is requested during the infusion time of LFG316 and up to 2 hours after the end of the infusion during Treatment Period 1. In case of a suspected infusion reaction (e.g. mild rash, general discomfort) the infusion rate should be reduced and vital signs should be monitored continuously. Infusion should be stopped in case of severe reactions with need for intervention, as judged by the investigator (e.g. treatment with glucocorticoids, histamine antagonists, epinephrine, bronchodilators). Pharmacokinetic parameters (measures of treatment exposure) will be determined in all subjects treated with LFG316, as detailed in [Section 8.5](#).

Applicable for period 4: LNP023 will be administered orally at the patients' home or at the study center (mandatory at days when PK samples are collected). During days 1-28 patients will be receiving both LFG316 every 2 weeks and LNP023 every day. On days 29-141 (+/-28 days), LNP023 will be administered as monotherapy. LNP023 dose diary will be implemented to capture information on missing doses. During the COVID-19 pandemic that limits or prevents on-site study visits, delivery of LNP023 directly to a patient's home is generally permitted in the event the Investigator has decided that an on-site visit by the patient is no longer appropriate or possible, and that it is in the interest of the patient's health to administer the study

treatment even without performing an on-site visit. Implementation will need to be discussed with Novartis. The dispatch of IMP from the site to the patient's home remains under the accountability of the Investigator. In this case, regular phone calls or virtual contacts (at the frequency matching planned study visit) will occur between the site and the patient for instructional purposes, safety monitoring, and discussion of the patient's health status until the patients can again visit the site.

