All pre-menopausal women who are not surgically sterile will have regular serum pregnancy test at screening and urine pregnancy tests at all other time points during the study. A positive urine pregnancy test requires immediate interruption of study drug until serum β -hCG is performed and found to be negative. Only for post-menopausal women hormone measurement (FSH) to confirm post-menopausal status is required at screening.

8.3.7 **Vaccination**

Vaccination will be performed according to local recommendations for patients with complement deficiencies, if prior vaccination cannot be confirmed. The choice of vaccine(s) should take into account the serotypes prevalent in the geographic areas in which study patients will be enrolled.

The meningococcal vaccine(s) should be administered at least two weeks prior to starting LFG316 and should be boosted during the study as per recommendation. If LNP023 treatment has to start earlier than 2 weeks post vaccination, prophylactic antibiotic treatment must be initiated.

For patients participating in period 4, vaccination for the prevention of *S. pneumoniae* and *H. influenzae* infections should be administered at least 2 weeks prior to first dosing with LNP023, as per local guidelines and regulations. If LNP023 treatment has to start earlier than 2 weeks post vaccination, prophylactic antibiotic treatment must be initiated. Based on local recommendations, revaccination at the start of LFG316 therapy should be considered for previously vaccinated subjects as well as during LFG316 and LNP023 therapy for subjects who will receive prolonged treatment.

Continuous close monitoring of subjects for early symptoms and signs of meningococcal infection is required in order to evaluate subjects immediately if an infection is suspected.

Comercially Confidential Information

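### In period 4 no pregnancy test is scheduled between Day 85 and Study Completion (63 days, of which 56 are on in-study LNP023), so no test after Day 85 can trigger the interruption rule during in-study treatment

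*Protocol*

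**What the plan says.** The period 4 table in Protocol Section 8 has columns for Days "1 15 29 36 43 57 85 141", followed by Study Completion, described as "Visit 777 Day 148 (1 week after last LNP023 dose) ±28". The visit windows are ±2 days at Days 57 and 85 and ±28 days at Day 141.

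The pregnancy row reads "Pregnancy test X ¹ X X X X". Cell by cell, the marks fall on Days 1, 29, 57, 85 and Study Completion. Days 15, 36, 43 and 141 are blank. The blood-hormone row has the same marks plus Day 141.

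On treatment timing, Section 6.7 states: "On days 29-141 (+/-28 days), LNP023 will be administered as monotherapy". Section 3.1 says that period 4 patients "will complete their Study Completion evaluation approximately one week after last LNP023 treatment administered as a part of this study". It also asks that patients who move to the extension study have no break in LNP023.

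On the test itself, Section 8.3.6 prescribes a serum test at screening and "urine pregnancy tests at all other time points during the study". It adds: "A positive urine pregnancy test requires immediate interruption of study drug", pending a negative serum result. Section 3.6.1 says that women of child-bearing potential must be told that "taking the study treatment may involve unknown risks to the fetus if pregnancy were to occur during the study".

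**The concern.** The interruption rule in Section 8.3.6 acts only on a positive test, so the longest interval between tests bounds how long a pregnancy could go without a scheduled check while drug is being given. In period 4 that interval more than doubles just as LNP023 becomes the only treatment and visits thin out: no visit of any kind is scheduled between Day 85 and Day 141. The Day 141 visit, the last on treatment, collects blood hormones but no pregnancy test. The one remaining test falls after the last in-study dose.

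If a woman conceives shortly after Day 85, no scheduled test prompts interruption for the rest of in-study monotherapy. If she rolls over, she continues LNP023 on the strength of a last in-study test that is nominally 56 days old.

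**Working it through.** **Inputs.** Visit days, windows and row marks come from the period 4 table in Section 8. The dosing period comes from Section 6.7. The timing of Study Completion relative to the last dose comes from Section 3.1 and the table.

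**The plan's own figure.** Section 3.1 gives period 4 as about 21 weeks, made up of 4 weeks of co-exposure and about 16 weeks of monotherapy, with Study Completion about a week after the last dose.
- Whole period: (148 − 1)/7 = 21.0 weeks
- Co-exposure: (29 − 1)/7 = 4.0 weeks
- Monotherapy: (141 − 29)/7 = 16.0 weeks
- Last dose to Study Completion: 148 − 141 = 7 days

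The table and the text agree, so the days can be relied on.

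**Alignment of the row.** The pregnancy row has nine cells for nine columns, and so does the blood-hormone row. The two match except at Day 141, which makes a shifted column unlikely.

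**Intervals.** Nominal = later day − earlier day. Maximum = (later day + its window) − (earlier day − its window). Minimum = (later day − its window) − (earlier day + its window).

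| From | To | Nominal | Minimum | Maximum |
|---|---|---|---|---|
| Day 1 | Day 29 | 28 | 27 | 29 |
| Day 29 | Day 57 | 28 | 25 | 31 |
| Day 57 | Day 85 | 28 | 24 | 32 |
| Day 85 | Study Completion, Day 148 | 63 | 120 − 87 = 33 | 176 − 83 = 93 |

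**Part of the last interval on in-study LNP023 (Day 85 to Day 141).** Nominal 141 − 85 = 56 days; minimum 113 − 87 = 26; maximum 169 − 83 = 86. The remaining 7 days follow the last in-study dose. The age of the last in-study test at roll-over around Day 141 is the same quantity: 56 days, range 26 to 86.

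**Comparison within the protocol.** Period 1 and early period 2 also test on Days 1, 29, 57 and 85. Most of the readable period 3 row is marked at every third two-weekly visit: 3 × 14 = 42 days. The nominal 63 days exceeds both spacings.

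**Effect of a Day 141 mark alone.** The longest interval becomes 141 − 85 = 56 days (maximum 86), followed by 7 days to Study Completion. The nominal interval shortens by 63 − 56 = 7 days and the maximum by 93 − 86 = 7 days. The gain is mainly that a test then exists at the last on-treatment visit.

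**The case against.** Several stronger readings are tempting, and the documents do not support them.

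- A reader might infer that all 63 days, or up to 93, are spent on LNP023. Study Completion is set a week after the last in-study dose, so the in-study figure is 56 days (26 to 86). For a roll-over patient the last week may be on extension-study drug, but that is governed by another protocol.
- A reader might infer that Section 8.3.6 is contradicted because it speaks of urine tests at every other time point. Read in context, it says which type of test is used after screening. Section 8.3 leaves timing to the assessment schedule, and the row also leaves Days 15, 36 and 43 unmarked. There is no contradiction.
- A reader might take 28 days as the study-wide standard. Period 3 mostly tests about every 42 days, so it is not.
- The hormone draw on Day 141 might seem to strengthen the case. It shows only that samples are already taken at that visit. The scheduled test is a urine test and does not depend on the draw.

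The case for leaving the schedule alone is that safeguards exist. Highly effective contraception is required, and Sections 7.1 and 9.5 require study drug to be stopped in pregnancy however it comes to light (for LNP023, Section 7.1 allows a taper to be considered). Roll-over needs confirmed eligibility, which may include a pregnancy test that these documents do not show. The wide window at Day 141 can also shorten the interval, and few women are involved.

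These points limit the size of the problem but do not remove it. Contraception lowers the chance of pregnancy without detecting one, and mandatory discontinuation starts only once the pregnancy is known. An entry test in the extension study cannot be assumed, and it would not cover the weeks before roll-over.

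**Conclusion.** The point holds as a minor safety correction. Between Day 85 and Study Completion there is an interval of 63 days (33 to 93) without a scheduled pregnancy test, of which 56 days (26 to 86) are on in-study LNP023. Earlier in the same row the spacing is 28 days, and no reason is given for the change. Because the only later test follows the last in-study dose, the interruption rule in Section 8.3.6 has no scheduled test to act on for the rest of in-study treatment.

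This rests on two assumptions: that the table cells align with the columns as described, which should be checked against the typeset page, and that visits stay within the printed windows. It makes no claim about testing in the extension study. About 10 patients were to be enrolled, and only women of child-bearing potential who enter period 4 are affected. The efficacy analyses are untouched.

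**What to change.** 1. Confirm whether the blank Day 141 cell in the pregnancy row is intended. If it is, state the reason.
2. Reconcile the Day 85 to Study Completion interval with the row's own earlier spacing and with the interruption rule in Section 8.3.6.
3. Mark the urine test at the existing Day 141 visit, so that a test is done at the last on-treatment visit before any roll-over.
4. Because step 3 alone leaves 56 days without a test, the sponsor should decide how the time between Day 85 and Day 141 is covered, and record that decision in the schedule.

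The cost is one schedule mark and one or two urine kits per woman of child-bearing potential. The Day 141 mark needs no new visit. If the sponsor chooses testing at home for the earlier weeks, those results would be self-reported.

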8.1 Informed consent procedures

Eligible subjects may only be included in the study after providing written (witnessed, where required by law or regulation), IRB/IEC-approved informed consent.

If incapable of doing so, in cases where the subject's representative gives consent, the subject should be informed about the study to the extent possible given his/her understanding. If the subject is capable of doing so, he/she should indicate assent by personally signing and dating the written informed consent document or a separate assent form.

Informed consent must be obtained before conducting any study-specific procedures (i.e. all of the procedures described in the protocol). The process of obtaining informed consent should be documented in the subject source documents.

The date of signing of informed consent (and withdrawal, if later withdrawn) should be documented in the CRF.

Novartis will provide to investigators a proposed informed consent form that complies with the ICH GCP guideline and regulatory requirements and is considered appropriate for this study. Any changes to the proposed consent form suggested by the investigator must be agreed to by Novartis before submission to the IRB/IEC.

If applicable, Pregnancy Outcome Reporting Consent for female patients will be implemented.

Commercially Confidential Information

In the event that Novartis wants to perform testing on the samples that are not described in this protocol, additional Institutional Review Board and/or Ethics Committee approval will be obtained.

A copy of the approved version of all consent forms must be provided to the Novartis monitor after IRB/IEC approval.

8.2 Subject demographics/other baseline characteristics

Subject demographic and baseline characteristic data will be collected on all subjects.

Relevant medical history/current medical conditions data includes data until signature of informed consent. Where possible, diagnoses and not symptoms will be recorded.

Investigators have the discretion to record abnormal test findings on the medical history section of the CRF whenever in their judgment, the test abnormality occurred prior to the informed consent signature.

Historical data of serum LDH may be recorded, if available, to help characterize disease status and progression.

8.3 Safety

Safety assessments are specified below; methods for assessment and recording are specified in the Site Operations Manual, with the [Assessment schedule](#) detailing when each assessment is to be performed.

8.3.1 Physical examination

8.3.2 Vital signs

- Body temperature
- Blood pressure (BP)
- Pulse

Blood pressure and pulse should be collected in a sitting position, after the subject has been sitting for 3 minutes.

8.3.3 Height and weight

- Height
- Body weight (to be used for ongoing dose calculation according to SOM instructions)
- Body mass index (BMI) will be calculated (Body weight (kg) / [Height (m)]²)

8.3.4 Laboratory evaluations

Clinically relevant deviations of laboratory test results that are considered unexpected in PNH patients, occurring during or at completion of the study must be reported and discussed with Novartis personnel. The results should be evaluated for criteria defining an adverse event and reported as such if the criteria are met. Repeated evaluations are mandatory until normalization of the result(s) or until the change is no longer clinically relevant. In case of doubt, Novartis personnel should again be contacted.

Hematology

Hemoglobin, hematocrit, red blood cell count, white blood cell count with differential and platelet count will be measured.

Clinical chemistry

Sodium, potassium, creatinine, urea, uric acid, chloride, albumin, calcium, alkaline phosphatase, total bilirubin, CRP, LDH, GGT, AST, ALT, aPTT, PT/INR, CK, glucose, total cholesterol, triglycerides.

- Bilirubin: Bilirubin is released during hemolysis and is frequently increased in PNH patients. Serum levels will be determined using standard procedures. If the total bilirubin concentration is increased above 3 times above the baseline value, direct and indirect reacting bilirubin should be differentiated.
- Ferritin: Ferritin levels have been reported to increase during treatment with eculizumab, and are a measure for iron overload. Serum levels will be determined using standard procedures.

- Blood hormones (For period 4 only):
 - Thyroid hormone levels including T3, T4, TSH and reversed T3.
 - Reproductive hormones: Testosterone, Dihydrotestosterone (DHT), Follicle stimulating hormone (FSH), Luteinizing hormone (LH)

Urinalysis

A semi-quantitative "dipstick" evaluation for the following parameters will be performed: specific gravity, pH, glucose, protein, bilirubin, urobilinogen, ketones, nitrite, leukocytes and blood/hemoglobin.

If the dipstick result is positive for protein, nitrite, leucocytes and/or blood the sample will be sent for microscopic analysis of WBC, RBC and casts.

8.3.5 **Electrocardiogram (ECG)**

PR interval, QRS duration, heart rate, RR, QT, QTc

The Fridericia QT correction formula (QTcF) should be used for clinical decisions.

8.3.6 **Pregnancy and assessments of fertility**

All pre-menopausal women who are not surgically sterile will have regular serum pregnancy test at screening and urine pregnancy tests at all other time points during the study. A positive urine pregnancy test requires immediate interruption of study drug until serum β -hCG is performed and found to be negative. Only for post-menopausal women hormone measurement (FSH) to confirm post-menopausal status is required at screening.

8.3.7 **Vaccination**

Vaccination will be performed according to local recommendations for patients with complement deficiencies, if prior vaccination cannot be confirmed. The choice of vaccine(s) should take into account the serotypes prevalent in the geographic areas in which study patients will be enrolled.

The meningococcal vaccine(s) should be administered at least two weeks prior to starting LFG316 and should be boosted during the study as per recommendation. If LNP023 treatment has to start earlier than 2 weeks post vaccination, prophylactic antibiotic treatment must be initiated.

For patients participating in period 4, vaccination for the prevention of *S. pneumoniae* and *H. influenzae* infections should be administered at least 2 weeks prior to first dosing with LNP023, as per local guidelines and regulations. If LNP023 treatment has to start earlier than 2 weeks post vaccination, prophylactic antibiotic treatment must be initiated. Based on local recommendations, revaccination at the start of LFG316 therapy should be considered for previously vaccinated subjects as well as during LFG316 and LNP023 therapy for subjects who will receive prolonged treatment.

Continuous close monitoring of subjects for early symptoms and signs of meningococcal infection is required in order to evaluate subjects immediately if an infection is suspected.

Comercially Confidential Information

